We found moderate-large reductions in fatigue at T1 in HS ($p < .01$)²⁸ (Table 2). The HS group continued reductions in fatigue at T2 ($p < .01$) (large effect), with no additional intervention, while fatigue increased in HH. There were no statistically significant differences in improvements in anxiety or depression at T1; but large improvements in anxiety in HS at T2 (effect size = 0.69, $p < .01$). Depression continued to improve in HS at T2,

but not HH. The CBT-I effect on depression was significant when adjusted for insomnia remission ($p = .02$). Pain did not improve, but was correlated with insomnia severity ($p < .01$), fatigue ($p = .02$), sleepiness ($p = .07$), and physical function ($p < .01$). Sleepiness was low in both groups (range 6.84-7.55), consistent with past research,⁵³ and may reflect sympathetic activation,⁵⁴ lack of recognition of sleepiness or insufficient sensitivity of the Epworth Scale. CBT-I effects on sleepiness will be evaluated with additional measures in this study.

Cluster analysis performed on symptom severity at T1 (pain, anxiety, depression, fatigue, dyspnea, sleepiness) revealed 3 clusters: I (all mild: $N = 25$), II (high pain/dyspnea: $N = 9$), III (high depression, anxiety, sleepiness: $N = 14$). Of those in insomnia remission at T1 ($ISI < 8$), 65% were in Cluster I, and only 10% were in Cluster III, while 42.3% of those with persistent insomnia were in Cluster III ($p = .054$). Functional performance was higher in Cluster I than II or III ($p < .0001$). These associations suggest the significance of our plan to examine the effects of CBT-I on changes in symptom cluster group membership.

After controlling for baseline symptoms, the estimated incidence rates of **cardiac hospitalizations** in one year were 11.7% and 18.7% in HS and HH, respectively; 9% of those with insomnia remission, compared with 27.8% with persistent insomnia were hospitalized. Taken together with fewer cardiac hospitalizations in those with mild symptom clusters vs. more severe clusters (Cluster I: 4.8%; Clusters II/III: 35%), these data suggest the greater benefits of CBT-I, compared with self-management education, to health care resource utilization.

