We will conduct cost-effectiveness analysis (CEA) from a societal perspective where all costs are considered, regardless of who incurs them,^{182,183} document resource use in units, and apply prices to units. Data will be obtained by self-report and validated through the EMR, hospital cost accounting database, and the Medicare fee schedule. Variables will include direct costs for health care resources used [office and emergency department visits, homecare, hospitalizations (and reasons, e.g., HF), cardiac devices, over the counter (OTC) and prescribed medications]. A sub-set of our team, blinded to group assignment, will review hospitalization/ED/office visits and evaluate causes. We will use the electronic pharmacy system to obtain prescription drug utilization and self-report for OTC medications. We will determine costs for prescription and OTC medications with Redbook average wholesale prices and public market prices from drugstore.com. We will include payments to the interventionists and costs of intervention materials. Deaths and causes of death will be ascertained with the EMR. If not found, we will query the National Death Index. Indirect costs will include self-reported time missed from work, travel, and self-management and CBT-I activities. We will measure effectiveness as quality adjusted life years (QALY), estimated from the EQ-6D algorithm from SF-36 data¹⁸⁴ and track research-related costs (monitoring, data collection, personnel costs, and subject payments).

Table 4. Primary Study Variables and Measures: *Baseline, 3 months, 6, 12 months*

Variable	Measure
Sleep/Insomnia	
Global Sleep Quality	Pittsburgh Sleep Quality Index (PSQI); PROMIS Sleep Disturbance Brief Item Bank
Sleep latency (SL), wake after sleep onset (WASO), efficiency (SE), time in bed (TIB), total sleep time (TST)	Subjective: PSQI Objective: Actiwatch2/Wrist Actigraph
Insomnia Severity	Insomnia Severity Index (ISI)
Symptoms	
Excessive Daytime Sleepiness	Epworth Sleepiness Scale (ESS); PROMIS Sleep Impairment Brief Item Bank
Fatigue (total, severity, distress, interference, timing)	Multi-dim Assessment of Fatigue Scale (MAFS)
Depressive Symptoms	PROMIS Depression Short Form 8a
Anxious Symptoms	PROMIS Anxiety Short Form 8a
Pain (severity, location, and interference)	PROMIS Pain intensity-3 item; PROMIS Pain Interference
Dyspnea (total, severity, distress, interference, timing)	Multi-dim Assessment of Dyspnea Scale (MADS)

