Data collection: Participants who meet the study criteria and agree to participate will complete a battery of questionnaires to elicit self-reported symptoms, functional performance, and characteristics of sleep. They will also complete forms to indicate their use of heart failure self-management and self-care behaviors. Participants will wear wrist actigraphs (accelerometer device that is approximately the size of a sports watch) for 2 continuous weeks, removing them only for bathing. They will be reminded not to cover the actigraph with clothing or bedclothes because this will obscure the light measurements. Participants will simultaneously complete a diary to note characteristics of sleep, use of hypnotic medications, and times of lights out and lights on related to sleep time, as well as removal (and reasons) of the actigraph. These data will be used to assist in scoring the actigraphy data, and participants will have the option to complete the diary on paper or on an electronic device. At the end of this screening period, participants will visit the Yale School of Nursing Biobehavioral Laboratory where they will complete a six-minute walk test and a psychomotor vigilance test.

The questionnaires, diaries, actigraphy, six minute walk, and psychomotor vigilance test will be repeated at baseline, 3 months (2 weeks after participating in the treatment/control conditions), and at 6 and 12 months.

In addition to the primary study variables noted above, medical records will be reviewed and participants will be interviewed over each of the study time periods to elicit changes in health status, medication use, any additional treatments, and use of health care resources (e.g., visits to health care providers, hospitalizations, emergency department visits, medications, as well as time off from work, time associated with use of the CBT-I and self-management skills practice, and other possible costs associated with the intervention and heart failure. These data will be obtained through the 12-month follow-up period.

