After the 12-month follow-up, a member of the study team will contact participants every 2 months until the end of the 5 year study period to obtain information on health status, hospitalization/emergency department visits (and their causes), possible heart transplants, or implantation of a left ventricular assist device in order to measure events used to calculate event free survival. This may result in between 18 and 45 months of follow-up depending on when participants are recruited into the study.

Intervention phase:

Participants will be randomized in groups of 6-8 into the intervention group (cognitive behavioral therapy for insomnia – CBT-I: “Healthy Sleep Group:”HH) or into a comparison group condition that will include information on self-management of heart failure and sleep hygiene information (“Healthy Hearts Group:” HH). Participants will not know the group to which they have been randomized until they arrive at the meeting. Participants in both groups will attend 4 bi-weekly face-face one-hour sessions and participate in 4 15-minute telephone calls (each of the 4 weeks alternating with the face-face sessions). The calls will consist of 1) reminders to continue using the strategies taught in the sessions 2) clarification of questions or problems with the prescribed activities (attention or control); 3) reminders/clarification regarding completion of the logs, and 4) reminders about the time and place for the next session. If unable to attend isolated group meetings, they will participate by telephone conference call or Skype. They will also be able to make up single sessions by telephone or Skype.

The CBT-I group will receive instruction on techniques to improve their sleep and be expected to practice these techniques at home. These techniques will be included over the 4 face-face meetings in which the therapist will teach and provide examples and feedback on individual progress with each of the activities. There will be an opportunity for questions and discussion. The therapist will provide feedback at each session. CBT-I includes stimulus control; sleep restriction, cognitive therapy, relaxation, and optional tapering of hypnotic medications. They will participate in a brief discussion covering HF medications, symptoms, management of fluids and when to call their health care provider about HF symptoms.

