Risks are highly unlikely. However, stimulus control therapy, a component of CBT-I requires the patient to get out of bed when sleepy. For frail patients, it is possible that this could result in falls. Sleep restriction may result in excessive daytime sleepiness and lower the seizure threshold for people who have undiagnosed epilepsy or bipolar disorder. However, we do not expect this to occur, as these are exclusion criteria. In addition, paradoxical anxiety reactions have rarely been reported as a result of relaxation therapy. It is possible, but unlikely that the group sessions, telephone calls, or interviews may elicit psychosocial distress in study participants. The clinicians leading the sessions include experienced advanced practice nurses who will refer participants for follow-up care as appropriate.

We may uncover sleep disordered breathing or psychiatric disorders, such as depression in the screening process. Participants with these conditions will be notified and suggestions will be made for follow-up care. All patients and referring providers will receive a written report of their sleep evaluations and depressive and anxious symptoms with recommendations for follow-up as needed. We will not send these reports to providers other than those referring to the trial because that would be a HIPAA violation. If our screening suggests that any patient may be suicidal, we will refer them immediately for follow-up.

2. Alternative Treatment

An alternative treatment for study participants is the use of hypnotic drugs. Other forms of behavioral treatment are available that include components similar to those in this study (relaxation, sleep restriction, sleep hygiene, etc.). Patients who are depressed or anxious and have insomnia may also benefit from pharmacological or behavioral treatment for these conditions. However, several studies have shown that CBT-I improves mood disorders with and or without additional pharmacological treatment.

Adequacy of Protection Against Risks

a. Recruitment and Informed Consent

1. Recruitment

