We will protect against the risks of the effects of the experimental condition by excluding patients who have bipolar disorder or seizure disorders, as well as those with Epworth Sleepiness Scale scores >18 due to the potential for sleep restriction to increase sleepiness and potential injury. In addition, we will not use sleep restriction below 4.5 hours to avoid extreme sleepiness. We will not include individuals with severe depression in either group. Participants will be carefully monitored for these and any changes in emotional distress, particularly anxiety and depression. The clinicians leading the groups are health professionals who are trained to observe for these issues. Participants will be instructed to call the research coordinator if they have worsening of their sleep, emotional distress, or increased severity of any symptoms over the course of the study. Participants will be referred to a mental health clinicians or the cardiology health care provider if they have any of these concerns. If new or exacerbated health problems, such as sleep apnea or depression, are detected during the study assessments, participants will be referred to their referring providers (or a provider of their choice) for follow-up evaluation and possible treatment.

All study participants and their referring health care providers will receive a report of their ARES sleep studies (measure of sleep disordered breathing) and a report of the depression screening with appropriate recommendations for treatment if indicated.

The risk of violation of confidentiality will be minimized by using documents with code numbers, linked only to the master list of participants that will be maintained in a physically locked file. Electronic records, including the patient logs, will be password protected and encrypted, consistent with Yale University policies. Only members of the study team will have access to the physical or electronic data.

Potential Benefits of the Proposed Research to Human Subjects and Others

a. Potential Benefits to Participants

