Potential benefits include learning more about sleep and improving insomnia, as well as self-management of heart failure. It is also possible that symptoms, including sleepiness, fatigue, anxiety, and depression, and daytime functioning may improve, especially in the experimental arm. Participants in the comparison group will learn about self-management of heart failure, including increased understanding of the disease process, medications, fluids, diet, sodium management, stress management and exercise, as well as basic information about sleep. It is possible that improvement in these behaviors may improve sleep/insomnia, as well as symptoms and functional performance. HF self-management information will be available to both groups through the Fight against Heart Failure Handbook.

b. Balance of Risks and Benefits

The risks of this study are minimal relative to the potential benefits.

Importance of the Knowledge to be gained

The knowledge obtained in this study may lead to important advances in understanding the outcomes of cognitive behavioral therapy for insomnia, an efficacious treatment in many populations that has been understudied among people with HF. Based on our preliminary work, we expect that CBT-I will reduce insomnia severity and lead to improvements and fatigue and possibly other symptoms related to insomnia and often experienced by HF patients. This study will also evaluate the impact of CBT-I on health care utilization and cost, as well as event-free survival. If, as we hypothesize, CBT-I has sustained efficacy and is cost-effective,

this study will provide critical evidence to support of future translational work in which we will conduct an effectiveness study focused on enhancing reach, adoption, implementation, and long term maintenance⁶⁵ (factors associated with sustainability) of CBT-I into diverse HF disease management settings. For example, this study may include structured online training for HF registered nurses; education on use of acceptable billing codes for insomnia and fatigue treatment; and strategies to integrate CBT-I into cardiac rehabilitation programs or HF support groups, among others.

Data Safety and Monitoring Plan

The risks are very minimal in this single-site study, therefore a data and safety monitoring board is not required.²⁰⁰ We had no adverse events in our previous study.

a. Monitoring entity or who will monitor the study (i.e., PI, ISM, SMC, or DSMB).

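### Falls and treatment-phase sleepiness are named as possible CBT-I harms, but the plan has no structured collection of either during the eight treatment weeks and no harms table by arm

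*Combined protocol and SAP*

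**What the plan says.** **The harms.** Potential Risks (Protection of Human Subjects) links stimulus control to falls and sleep restriction to sleepiness: "For frail patients, it is possible that this could result in falls. Sleep restriction may result in excessive daytime sleepiness". The section on minimizing risk takes this seriously. It excludes people with high Epworth scores, citing possible injury, and limits how far sleep is restricted.

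**Contacts during treatment.** Table 1 places calls in weeks 2, 4, 6 and 8. Their content is set out under Intervention phase, beginning "The calls will consist of 1) reminders to continue using the strategies taught in the sessions" and going on to clarification of questions or problems with the activities, log completion, and the next session.

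**Self-report to staff.** "Participants will be instructed to call the research coordinator if they have worsening of their sleep, emotional distress, or increased severity of any symptoms". Falls are not named in this instruction. Group leaders are said to be trained to observe for problems, but no form or schedule is given.

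**Formal measures.** Table 4 lists "Epworth Sleepiness Scale (ESS); PROMIS Sleep Impairment Brief Item Bank" for daytime sleepiness, on the schedule "Baseline, 3 months, 6, 12 months". The Data collection text under Human Subjects Involvement confirms that questionnaires and the vigilance test "will be repeated at baseline, 3 months (2 weeks after participating in the treatment/control conditions), and at 6 and 12 months".

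**Analysis.** The Statistical Analysis Plan compares sleepiness and vigilance between arms as outcomes, including an Epworth cutoff of 10 or more. It contains no adverse-event or harms analysis.

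**The concern.** Both named harms would be expected mainly while participants are getting out of bed at night and restricting time in bed, that is, in weeks 1 to 8. Sleepiness that rises during restriction and settles by the post-treatment visit would be missed by every formal measure. A fall that leads to no medical visit has no question that asks for it by name.

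This matters because the trial's rationale is partly comparative safety. The Specific Aims list daytime sleepiness and falls among the harms of hypnotics and describe CBT-I as free of negative daytime effects. A final report with few or no falls in the CBT-I arm could be read as support for that view when nobody had asked the question.

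**Working it through.** The plan states no figure on this point, so there is none to reproduce. The check is a comparison of the text, followed by three illustrations.

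**1. What each contact or measure collects**

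| Source | When | Falls by name | Sleepiness |
|---|---|---|---|
| Treatment calls (Intervention phase) | Weeks 2, 4, 6, 8 | No | Not listed |
| Daily logs, both arms (Approach) | Treatment weeks, reviewed at each session | Not listed | Symptoms logged; items not visible to us |
| Monthly calls (Follow-up data collection) | After treatment to month 12 | No; health-status changes and service use elicited | Not listed |
| Interviews and record review (Data collection) | Each study period | No; health-status changes elicited | Not listed |
| Epworth, PROMIS impairment, vigilance test | Baseline, 3, 6, 12 months | – | Yes, but not in weeks 1–8 |
| Blinded review of hospital, emergency and office visits | As they occur | Only if medical care is sought | Only if medical care is sought |

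The only other mention of falls is in the Specific Aims, as a harm of hypnotics. Some sections speak of five data collection periods, but only four time points are listed and none lies within treatment.

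The call descriptions also conflict. The Approach says the monthly calls repeat the content of the treatment calls apart from meeting reminders. Intervention phase and Follow-up data collection give different lists for the two. Which text governs decides whether health-status changes are elicited during treatment.

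**2. What zero recorded falls would exclude**

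Inputs: n = 100 per arm (Sample Size); capture proportion c is my assumption. If the true risk is p, the chance of recording none is (1 − pc)^100. Setting this to 0.05 gives p = (1 − 0.05^(1/100))/c = 0.0295/c.

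- c = 1: 2.95%, about 3%
- c = 0.8: 0.0295/0.8 = 3.7%
- c = 0.5: 0.0295/0.5 = 5.9%, about 6%
- c = 1/3: 0.0295 × 3 = 8.9%, about 9%

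**3. If capture differed between arms**

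With equal true risk, the apparent risk ratio is the ratio of the capture proportions. Assumed capture of 80% in CBT-I and 50% in control gives 0.8/0.5 = 1.6. The reverse gives 0.5/0.8 = 0.625. The error could go either way, and the documents do not fix its direction.

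**4. What a between-arm comparison could show**

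Assume fall risks of 10% and 20%, 100 per arm, two-sided 5%.

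- Full capture: pooled standard error √(2 × 0.15 × 0.85/100) = 0.0505; unpooled √((0.09 + 0.16)/100) = 0.0500. Power = Φ((0.10 − 1.96 × 0.0505)/0.0500) = Φ(0.02) = 51%.
- Half captured in each arm (5% against 10%): pooled 0.0372, unpooled 0.0371. Power = Φ((0.05 − 1.96 × 0.0372)/0.0371) = Φ(−0.62) = 27%.

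Even complete data would be descriptive, not a powered safety test.

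**The case against.** The strongest reply is that the plan does not simply wait for participants to ring in. Both arms keep daily logs that include symptoms, and staff review them at each session. Study-period interviews elicit health-status changes, so the 3-month interview covers the treatment weeks. The causes of hospital, emergency and office visits are reviewed by team members blinded to arm, which gives medically attended falls a common route. Treatment calls invite problems with the prescribed activities. There is an adverse-event tracking tool and a quarterly Adverse Events Committee. The log items and call scripts are not in the documents available here, so the logs may cover sleepiness. All of this stands, and it narrows the gap.

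Two stronger readings are tempting, and neither is supported.

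- A reader might infer that harms rest on volunteered reports that differ by arm. The channels above are solicited and present in both arms, contact time is equal by design, and the instruction to call is the same for everyone. Some features could produce unequal capture: only CBT-I sessions review sleep diaries and adjust the sleep schedule, and each arm has its own interventionist. The Approach lists sleep only for the CBT-I log, but Potential Risks describes log entries for participants generally, sleep included. A difference is therefore possible but not shown.
- A reader might set "We had no adverse events in our previous study" against the pilot's cardiac hospitalization rates, which "in one year were 11.7% and 18.7% in HS and HH, respectively", and conclude that passive capture failed. Pilot hospitalizations were actively elicited, at 6 and 12 months, and were reported. The rates are model-adjusted estimates, not counts. The two statements may differ only in what was classed as an adverse event, which the documents do not define.

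**Conclusion.** The point holds in a limited form. Falls and excessive sleepiness are named as possible harms of CBT-I components, yet neither has prespecified structured collection during the treatment weeks. No listed contact asks about falls by name, and the SAP plans no between-arm harms table. What is uncovered is mainly falls without medical care and formal sleepiness data in weeks 1 to 8. Sleepiness from 3 months on is properly compared between arms as an outcome.

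The consequence is that an absence of recorded falls would be weak evidence. The upper bound on risk would lie between about 3% and 9% for capture between 100% and one third. Those capture rates are assumptions, and 100 participants per arm is the planned number. If the log items or call scripts already ask about falls and sleepiness, the data gap closes, and what remains is to list these items in the plan and tabulate them by arm. This is a cheap improvement worth making; it does not undermine the efficacy analysis.

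**What to change.** 1. Add the same fixed items, in the same words and in both arms, to the existing calls at weeks 2, 4, 6 and 8 and monthly to month 12: number of falls since the last contact, whether any caused injury (yes/no), and a brief sleepiness rating.
2. List these items among the collected data, in Table 4 and in the description of data under Protection of Human Subjects.
3. Add to the SAP a descriptive table by arm, separating the treatment weeks from later follow-up: participants with at least one fall, number of falls, injurious falls, and sleepiness ratings at each call. Show numbers contacted as denominators.
4. Reconcile the description of the calls in the Approach with those under Intervention phase and Follow-up data collection, so that one text states what is elicited during treatment.

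The cost is one or two minutes on scripted calls (about 10 minutes in the Approach, 15 under Intervention phase), one set of REDCap fields and a minor amendment. No new visits or staff are needed.
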